The post-intervention assessment consists of one depressive symptom measure, so no remuneration will be provided. Baseline and follow-up data will be collected and managed using REDCap (Research Electronic Data Capture), a secure web-based application designed to support data capture for research studies, hosted and supported by Northwestern’s Clinical and Translational Science Institute. Once research staff enters participant contact information, REDCap will generate emails or texts containing web-based survey links at scheduled time points. Baseline data will be collected within 2-3 weeks of establishing client eligibility and participation agreement. Women who do not complete the web-based baseline assessment in this timeframe will be contacted by phone by the Research Coordinator to complete the assessment either by phone or online, ensuring that baseline data are collected prior to the first MB group. Informed consent will be obtained prior to administering the baseline assessment. If a study participant decides that they do not want to consent to participate in this study, no data will be collected from this participant. For the post-intervention, 12-week postpartum, and 24-week postpartum assessments, study participants who do not complete web-based assessments within one week of the web link being sent to them will be contacted by the research team to complete the assessments by phone.

Table 4 describes this study’s outcome indicators, measures, and data collection timelines.

Outcome Indicator	Measure	Baseline	Post-Intervention	12 weeks postpartum	24 weeks postpartum
Depressive Symptoms	Edinburgh Postpartum Depression Scale	X			
Current & Lifetime Major Depressive Episode	Maternal Mood Screener (MMS)	X		X	X

DEPRESSION					
Depressive Symptoms*	Quick Inventory of Depressive	X	X	X	X
Symptomatology					
PROXIMAL OUTCOMES					
Behavioral Activation	Behavioral Activation	X		X	X
Pleasant Activities	Pleasant Activities Schedule	X		X	X
Mood Regulation	Negative Mood Regulation Scale	X		X	X
Social Support	MOS Social Support Survey	X		X	X
Decentering	Experiences Questionnaire	X		X	X
Relationship w/Partner	Dyadic Adjustment Scale	X		X	X
Responsive and Reactive Parenting	Parental Cognitions and Conduct toward the Infant Scale			X	X
Subjective Well-Being	Flourishing Scale	X		X	X
Perceived Stress	4-item Perceived Stress Scale	X		X	X
PRENATAL HEALTH BEHAVIORS					
DEMOGRAPHICS					
INTERVENTION SKILL USE					
INVOLVEMENT IN PRENATAL SERVICES					

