Specific Aim #2 is to conduct a non-inferiority trial that compares the effectiveness of MB delivered by (a) mental health clinicians versus (b) paraprofessional home visitors.

Specific Aim #3 is to evaluate whether effectiveness of the two versions of MB (clinician led vs. paraprofessional home visitor led) varies according to patient characteristics (e.g., race, ethnicity, first-time mother, and/or geographic type of home visiting (HV) program (i.e., urban vs. rural).

Specific Aim #4 is to examine the feasibility and acceptability of MB delivered by paraprofessional home visitors and mental health clinicians.

Study time points include: baseline, immediately following the intervention period (or roughly eight weeks post enrollment for controls), 12 weeks postpartum, and 24 weeks postpartum. Primary time point of interest will be 24 weeks postpartum. This analysis plan will focus on the primary results manuscript, and thus, we will focus on Aims #1-#3.

Study Outcomes

Primary Outcome

Primary outcome of interest for Aims #1-#3 will be the Quick Inventory of Depressive Symptoms (QIDS-SR16) score as determined by participant self-report at 24 weeks postpartum. We will control for baseline QIDS-SR16 score. This is a continuous measure ranging from zero to 27 points, where higher scores signify increased depressive symptoms. QIDS-SR16 translates into depressive categories such that a score of less than five points indicates no depression, a score ranging from six to 10 indicates mild depression, 11-15 signifies moderate depression, 16-20

indicates severe depression, and anything above 20 would be labeled as very severe (<http://www.ids-qids.org/>). As a result, we deem a five-unit change or difference in score to be meaningful (as a jump in five points would result in an increase in depression severity tier for any individual patient).

Secondary Outcomes

The following secondary outcomes will further be examined in order to address subcomponents of specific aims and also to address some of the exploratory aims. These secondary outcomes align with key components of the Mothers and Babies intervention.

1. Incidence of major/clinical depression (major depressive episode [MDE])
 - a. A major depressive episode will be defined via the Maternal Mood Screener
 - b. MDE for the purposes of this study is defined as:
 - i. The participant indicates at least **five** of the problems listed within the past two weeks (part B on the form), **and**

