Analyses will proceed at the participant level. Primary analyses for QIDS-SR16 score at 24 weeks postpartum will involve all the participants in the study contributing data at this time point. Primary analyses will involve a linear mixed model for continuous outcome with independent fixed effect variables of baseline QIDS-SR16, study arm (three-level factor), and the baseline covariates listed above. We will report both covariate-adjusted and unadjusted estimates for intervention effect. Secondary analysis will be performed on those participants considered at risk at baseline (i.e., excluding the participants who do not meet the criteria for MDE as defined above). We plan to account for clustering effects via inclusion of a random site effect, which will allow for distinction of between and within-site variance. We will also explore inclusion of a random 'facilitator' effect as it is possible participants exposed to the same facilitator may have correlated responses. Intra-cluster correlation coefficients will be estimated via variance components estimates.

Intervention effect will first be evaluated via the adjusted Wald type III test for significant study arm effect at the 5% level of significance. If arm is significant at the 5% level, analyses evaluating the **superiority (Aim #1)** of HV-led intervention vs. control will proceed with Tukey's correction for multiple pairwise hypothesis tests. Assuming the Tukey-adjusted p-value for this comparison falls below the 5% level of significance in favor of the HV-led arm, **non-inferiority (Aim #2)** will further be assessed (using Tukey's correction) via pairwise comparison of adjusted 24-month QIDS in HV-led vs. MH-led arms. Figure 1 below depicts the margin and zone of non-inferiority for this comparison.

[figure not shown]

Figure 1. Margin of Non-inferiority (NI)

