The double-sided arrows represent 95% confidence intervals for the model-estimated adjusted mean 24-week difference in QIDS-SR16 score. Note that higher score signifies more depressive symptoms; thus if the estimated difference (HV minus MH score) is larger than zero, the HV arm has on average worse depressive symptoms. Since the pre-specified margin of non-inferiority is two units on the QIDS-SR16 scale, we will claim non-inferiority if the upper limit of the adjusted 95% confidence interval for the HV-led arm minus the MH-led arm comparison remains below two. The red arrows indicate scenarios in which we cannot claim non-inferiority and the blue arrows indicate scenarios in which the criterion for non-inferiority is met.

Using the same analytic approach, we will explore the addition of covariate-by-arm interaction terms in the aforementioned model or a three-way covariate-by-arm-by-time interaction term in the longitudinal modelling in order to explore whether effectiveness of intervention varies by patient characteristics (Aim #3). The covariates to be explored include: race/ethnicity, first-time mother, language, education, and use of mental health services at baseline. These analyses are more exploratory in nature, and thus power/sample size considerations do not focus on interaction effects. As a result, we anticipate evaluating interaction effects at the 10% level of significance without adjustment for multiple hypothesis tests. Qualitative data analysis methods will evaluate feasibility and acceptability of MB in each setting (Aim #4), and the details of these analyses will be specified elsewhere.

Additional analyses surrounding Aims #1-#3 will employ longitudinal methods, utilizing all study data at all time points (i.e., inclusion of a fixed study time point effect). Secondary outcomes will all be analyzed in this fashion with the exception being binary response variables (e.g., depression onset). In these cases, appropriate link and distributional assumptions (logit, binomial, respectively) will be specified. For the participants receiving active intervention (either HV-led or MH-led Mothers and Babies), we will examine a 'dose' variable in relation to outcomes. This dose variable will be defined as the number of sessions (out of six possible) attended for an individual participant.

Analytic Dataset

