Analyses will be conducted on the modified intent-to-treat (mITT) dataset whereby all participants randomized with data at the 24-week time point will be analyzed according to arm to which they were allocated. We will further perform a sensitivity analysis on the 'as treated' dataset. Those in either active intervention arm will be considered 'treated' if they attend at least four out of the six sessions required for the Mothers and Babies course. For participants with missing data at baseline and non-missing data at follow-up, we plan to impute mean baseline values from the participants' follow-up in order to allow for inclusion in analyses.

Power and sample size considerations allowed for some missing data and, as specified in our approved research plan, we have allowed for up to two clusters to drop out of each arm; however, in the event of large amounts of missing data (i.e., more than 15%), multiple imputation analyses will be explored. We will examine rates of missing data for all variables and determine whether the rates vary by participant characteristics, HV program location, or intervention arm. These summarizations will inform potential biases resulting from missing data. The mixed effects models planned for analysis are generally robust for unbalanced data across study time points. We plan to apply multiple imputation in order to account for missing data; we will impute at least five datasets to generate an estimated average intervention effect. These analyses will again serve as sensitivity analyses to the previously outlined analyses. For participants missing individual items on a particular assessment, we plan to randomly sample from the non-missing empirical distribution for that item. We anticipate less than 5% of participants that would require this imputation of individual items. Again, in the event of large amounts of missing individual items, we will explore multiple imputation methods.

Power and Sample Size Considerations

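### The primary 24-week analysis drops women without a 24-week QIDS and leaves the interim QIDS scores out of the model, so it can be biased if symptom-related dropout differs by arm

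*SAP*

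**What the plan says.** The SAP fixes the primary population twice. Under Statistical Methods, the analysis of 24-week QIDS-SR16 "will involve all the participants in the study contributing data at this time point". Under Analytic Dataset, the modified intent-to-treat rule is that "all participants randomized with data at the 24-week time point will be analyzed according to arm to which they were allocated". The primary model is a linear mixed model with "independent fixed effect variables of baseline QIDS-SR16, study arm (three-level factor), and the baseline covariates listed above", plus a random site effect. It has one outcome visit per woman.

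QIDS is collected at two visits in between. The SAP's introduction lists the follow-up times as "immediately following the intervention period (or roughly eight weeks post enrollment for controls), 12 weeks postpartum, and 24 weeks postpartum". Table 4 of the protocol (section 4.0) marks QIDS at baseline and all three follow-ups, and the same section explains that "The post-intervention assessment consists of one depressive symptom measure".

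The plan does use these scores, but not in the primary estimate:

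- Longitudinal models: "Additional analyses surrounding Aims #1-#3 will employ longitudinal methods, utilizing all study data at all time points".
- Multiple imputation with at least five datasets: "These analyses will again serve as sensitivity analyses to the previously outlined analyses". The variables in the imputation model are not given.
- A descriptive check of missingness by participant characteristics, programme location and arm.

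**The concern.** A completer model adjusted for baseline is safe when dropout depends only on arm and the baseline covariates in the model. If women leave because of how they felt after the intervention or at 12 weeks, those who remain at 24 weeks are a selected group, and baseline adjustment does not undo that. If the selection differs between arms, the contrast shifts.

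Two decisions rest on this model. Superiority of home-visitor-led delivery (HV) over usual care is tested first. If it is shown, non-inferiority to clinician-led delivery (MH) is judged by one confidence limit against 2 points. A few tenths of a point are small beside the 5-point difference used to power superiority, but not beside a 2-point margin.

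The other analyses do not protect the primary estimate. The modified intent-to-treat rule is written for analyses in general, so it may also remove women without a 24-week score from the longitudinal models, against the statement that all data at all time points are used. The SAP's remark that mixed models cope with unbalanced data across time points does not apply to a model with one outcome visit.

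**Working it through.** **1. The plan's own figure.** Inputs from the SAP's Power and Sample Size Considerations: SD 6, margin 2, ICC 0.01, 16 sites per arm, 23 analysed per site (27 × 0.85 = 22.95), significance level 1.7%.

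SE = 6 × √{[1 + (23 − 1) × 0.01] × 2 / (16 × 23)} = 6 × √(1.22 × 2 / 368) = 0.49.

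A noncentral t with 2 × (16 − 1) = 30 degrees of freedom and two-sided 1.7% gives 93.4% power, which agrees with the stated figure of over 90%. The same method reproduces all 12 entries for N per site for analyses in the SAP's sample-size table. The power calculation is not in dispute. It allows for attrition as a loss of numbers, not as a source of bias.

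**2. How large could the bias be?** The documents give no dropout by arm and no correlation between visits, so this step rests on assumptions. I simulated four QIDS scores per woman with SD 6, visit correlations of 0.45–0.65, no true effect, and a logistic dropout model before week 24 driven by the 12-week score. The completer model adjusted for baseline was compared with one that also uses the interim scores. A negative sign means that the first-named arm looks better than it is.

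| Dropout assumption | Completer bias (points) |
|---|---|
| Same rate and same symptom slope in both arms (15% or 29%) | 0.00 to 0.02 |
| 20% v 15%, same slope | about −0.1 |
| 20% v 10%, same slope | −0.21 |
| 29% v 15%, same slope | −0.18 to −0.30 |
| 15% in both arms, symptom-related in one only (log-odds 0.5–1.0 per SD) | −0.18 to −0.34 |
| 25% symptom-related v 15% random | −0.53 |
| 29% symptom-related v 15% random | about −0.6 |

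Using the interim scores left the bias within ±0.03 throughout.

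In a second set (correlations 0.5–0.7), one common dropout rule acted on arms that truly differ by 2–5 points. The completer bias was 0.05–0.10 towards the null at about 15% dropout and 0.06–0.19 at about 30%. In the same set, symptom dependence in opposite directions in the two arms gave 0.34–0.44 at 15% and 0.69–0.85 at 30%. Nothing in the documents points to that pattern, and I do not rely on it.

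**3. Effect on non-inferiority.** If the true HV minus MH difference is exactly 2 and the estimate is biased by b, the chance that the upper limit falls below 2 is Φ(−b/SE − c). Here c = 1.96 unadjusted, or 2.34 for Tukey with three arms.

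| b | −b/SE | Unadjusted 95% limit | Tukey limit |
|---|---|---|---|
| 0 | 0 | 2.5% | 1.0% |
| −0.2 | 0.41 | 6.1% | 2.7% |
| −0.4 | 0.82 | 12.7% | 6.4% |

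The SAP calls for Tukey's correction, so the last column is nearer to the plan. The figures describe the non-inferiority test alone. Because superiority must be shown first, the overall chance cannot be higher. Randomization Methods counts 15 HV and 16 MH sites. With those, SE = 6 × √[1.22 × (1/345 + 1/368)] = 0.50, which changes little.

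**4. Effect on superiority.** With 15 HV and 6 control sites of 23 women, SE = 6 × √[1.22 × (1/345 + 1/138)] = 0.67. A bias of −0.4 raises a false finding for HV at the Tukey limit from 1.0% to Φ(0.4/0.67 − 2.34) = 4.1%. Against the 5-point design difference, 0.4 is 8%.

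**The case against.** A reader might infer that dropout related to earlier symptoms necessarily biases both primary contrasts. The documents do not support that. With the same rate and the same dependence in both arms and no true difference, the contrast bias is about 0, and no dropout by arm is reported. Dependence on baseline and arm alone is sufficient for an unbiased contrast, not necessary.

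A reader might also infer that the plan ignores the interim scores. It does not: longitudinal models, multiple imputation and a check of missingness by arm are all written in. Section 4.0 of the protocol follows every woman to 24 weeks whatever her attendance, with intensive contact.

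Third, the larger biases need random loss in one arm and symptom-driven loss in the other, at rates up to 29% against the planned 15%. HV and MH women receive the same six-session course and the same follow-up, so such asymmetry is harder to suppose between them than between HV and usual care. A bias derived for HV versus usual care should not be read as a share of the HV–MH margin.

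Fourth, the near-zero bias after the change is partly built in, because dropout was generated from a score that the second model uses. Intermittent gaps, plausible since the post-intervention survey is unpaid, were not simulated.

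All four limit the size and certainty of the point. None supplies a safeguard for the primary estimate, because the analyses that use the interim scores are additional or sensitivity analyses and no result from them changes it.

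**Conclusion.** The point stands in conditional form. The primary analysis can be biased if symptom-related dropout differs by arm, or if a common dropout rule acts on arms with different interim symptoms. Under the stated assumptions the size runs from about 0, through roughly 0.1–0.35 points for modest arm differences, to about 0.6 in an extreme asymmetric case. The direction is not known in advance: it favours whichever arm loses more of its symptomatic women. The consequence is greatest for the non-inferiority limit, where −0.2 or −0.4 multiplies the chance of a false claim at the margin about 2.7-fold or 6.4-fold at the Tukey limit. It is smaller, though not nil, for superiority. The bias sizes depend on assumed correlations and dropout models. Only the SD, margin, ICC, site numbers and attrition come from the SAP. This is a worthwhile, low-cost improvement, not evidence that the planned result will be wrong.

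**What to change.** - Make the planned longitudinal mixed model primary: all women with any post-baseline QIDS, arm-by-visit terms, baseline QIDS and the listed covariates, a within-woman covariance across visits (unstructured if it can be fitted), and random site. Take the 24-week HV–control and HV–MH contrasts from it.
- State in Analytic Dataset that women without a 24-week score are included in this model.
- Keep the 24-week completer model as a sensitivity analysis.
- Reconcile the two multiple imputation statements in Analytic Dataset (one only explores it above 15% missing, the other plans to apply it), and name interim QIDS, arm and site among the imputation variables.

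The cost is SAP wording and some extra modelling, with no new data. Technical Details already provides for documented changes, which should be made before the database lock. The drawback is a more complex model that still assumes dropout is explained by observed data (missing at random).

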month prior to implementation, we will train home visitors and mental health professionals on MB. We will stagger implementation in two waves so that only half the sites are implementing at once. This will allow our Intervention Coordinator to focus her efforts on ensuring attendance at intervention groups and fidelity to intervention protocols. Study recruitment and implementation of all prenatal MB sessions will be completed by the 4th quarter of Year 2. This recruitment schedule will allow us to complete all postnatal MB sessions and follow-up data collection by the middle of Year 3, allowing study investigators to analyze data and prepare to disseminate study findings to both academic and community stakeholders.

Participant Screening: Participants will initially be screened for eligibility criteria by their home visiting program sites. Upon permission from the potential study participant, program sites will fill out a referral form, which will include the potential study participants name and contact information, and send it to the research team. Once the program sites refer potential study participants, a member of the study team will call the participant using the “Phone Script for Referrals” to screen the potential study participant for eligibility criteria and move forward with the consent process either via telephone or REDCap survey link.

Participant Outcomes Surveys: Participant outcomes will be collected at four time points—baseline, post-intervention, 12 weeks postpartum, and 24 weeks postpartum. Participants will receive \$20 remuneration at the baseline, 12-week and 24-week assessments. The MMS and EPDS will be administered to all clients during their baseline surveys. This information will be used for data analytics but not as an exclusion criteria. Data will only be collected from study participants who have consented to participate in the study.

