4. Of those that meet acceptable levels of imbalance, we randomly select one allocation for use in the current study.

We chose the p-value corresponding to the Kruskal-Wallis test (nonparametric version of an Analysis of Variance [ANOVA]) as our criterion for 'balance' in step #3 above. If the p-value for each of the three variables is larger than 0.30 for a given simulated allocation scheme, that particular allocation is deemed 'acceptable'. This criterion is adapted from the 'Minimal Sufficient Balance' principle from Zhao et al. [3] in the individual sequential randomization literature.

In the current study, randomization occurred in three waves for logistical purposes. The first included 14 sites (2 C:6 HV:6 MH); the second included 19 sites (4 C:7 MH:8 HV); allocation ratio was slightly off in this wave to account for dropout sites); and the third wave included 12 sites (1 C:6 MH:5 HV). Thus, we randomized a total of 45 sites in three waves; randomization of 42 sites was the study goal, reflected in our approved research plan. However, to account for site dropping out in the meantime, we adapted the algorithm to increase the number of sites randomized and also to allow for slightly discrepant allocation ratios than the planned 1:3:3 within each wave.

After randomization, eight programs dropped out, thereby yielding a total of 37 study sites contributing data for analyses. Data collected from all study participants will be used in the analysis. Among the 37 active study sites, 16 HV programs received the MB intervention delivered by mental health professionals, 15 received MB intervention delivered by HV paraprofessionals, and six programs serve as control sites. As an aside, 29 intervention sites ended up implementing at least one cohort (15 MH, 14 HV).

Statistical Methods

Descriptive statistics will summarize baseline characteristics (both site-level and participant-level) overall and by arm. As appropriate, mean \pm standard deviation (or median [inner quartile range]) will be used in cases of skewed or non-normal empirical distributions) and frequency (proportions) will summarize continuous and categorical data, respectively. Analyses will employ normal theory methodology as appropriate, and in cases of violations of assumptions, transformations and/or nonparametric analyses may be utilized.

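### The SAP's 24-week data requirement is not limited to the primary model, and so conflicts with its all-data rule for the longitudinal and secondary-outcome models

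*SAP*

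**What the plan says.** Outcomes are measured repeatedly. The Protocol (Procedures Involved) states: "Participant outcomes will be collected at four time points—baseline, post-intervention, 12 weeks postpartum, and 24 weeks postpartum". In its Table 4 the QIDS is taken at all four visits. The Maternal Mood Screener and the secondary scales (behavioral activation, social support, mood regulation, decentering) are taken at baseline, 12 and 24 weeks.

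The SAP then makes three statements about who is analysed.

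- Statistical Methods, primary model: "Primary analyses for QIDS-SR16 score at 24 weeks postpartum will involve all the participants in the study contributing data at this time point".
- Statistical Methods, supportive and secondary models: "Additional analyses surrounding Aims #1-#3 will employ longitudinal methods, utilizing all study data at all time points". On the secondary outcomes it adds: "Secondary outcomes will all be analyzed in this fashion with the exception being binary response variables". For those binary outcomes it specifies a logit link and a binomial distribution, not a different population.
- Analytic Dataset, where the modified intention-to-treat set is named for the analyses at large, with no limit to the primary model: "all participants randomized with data at the 24-week time point will be analyzed according to arm to which they were allocated". The only other set defined there is the as-treated set, for a sensitivity analysis.

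The Analytic Dataset section also remarks: "The mixed effects models planned for analysis are generally robust for unbalanced data across study time points". It plans multiple imputation, as a sensitivity analysis, and a review of missing-data rates by participant characteristics, program location and arm.

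**The concern.** Consider a woman with baseline, post-intervention and 12-week data who never completes the 24-week survey. The Statistical Methods section puts her in the longitudinal QIDS-SR16 model and the secondary-outcome models. The Analytic Dataset section, read as written, takes her out of both. Two programmers could build different datasets and each cite the SAP, and the choice could be made after results are known.

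Under the restrictive reading, the earlier-visit contrasts (post-intervention and 12 weeks for QIDS-SR16, 12 weeks for the secondary outcomes) are conditioned on a response given later. The longitudinal QIDS-SR16 model would also lose most of its value as a check on dropout, because it would contain the same women as the single-visit primary model. The Table 2 shell, which the SAP says is not binding, has columns for HV versus control and HV versus MH estimates beside rows for the earlier visits, so these contrasts may well be published.

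**Working it through.** **1. The plan's own figures.** From the SAP's power section: SD 6, 27 women recruited per site, 15% attrition, 23 analysed, ICC 0.01, 16 sites per MB arm, margin 2 points, significance level 5%/3.

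- Analysable per site: 27 × 0.85 = 22.95, i.e. 23.
- SE of HV − MH = 6 × √[2 × (1 + 22 × 0.01)/(16 × 23)] = 0.489.
- Power for the 2-point margin (noncentral t, 30 df, two-sided 5%/3; the SAP does not state sidedness) = 93.3%. This agrees with the stated figure of over 90%, so the same inputs can be used below.

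**2. Women at stake.** 27 − 23 = 4 per site. At 37 sites that is 148 of 999 women; at 38 sites (the power section's count) it is 152 of 1026. This is a ceiling. It assumes that all attrition falls between the 12-week and 24-week surveys, since women lost earlier have no 12-week data to discard.

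**3. Precision at 12 weeks.** SE = 6 × √[(1 + (m − 1) × 0.01) × (1/(k₁m) + 1/(k₂m))], with 16 sites per MB arm and 6 control sites.

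| Contrast | All 27 per site | Restricted, 23 per site | Ratio |
|---|---|---|---|
| HV − MH | 0.458 | 0.489 | 1.07 |
| HV − control | 0.620 | 0.662 | 1.07 |

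The restriction raises the SE by about 7%. This needs no assumption about why women drop out, only about when.

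**4. Possible bias at 12 weeks.** The documents give no dropout mechanism, so each row below is an assumption: SD 6, 15% missing at 24 weeks, everyone seen at 12 weeks, no covariate adjustment. Except in the last row, the symptom-related mechanisms use a logistic model with log-odds of dropout rising by 1 per SD of the 12-week score. Analysing everyone seen at 12 weeks gives no shift under any of them.

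| Dropout before 24 weeks | Shift in the restricted 12-week contrast |
|---|---|
| Completely random | 0 |
| Symptom-related, same in both arms, no true effect | 0 |
| Same mechanism, true effect −2 | −2.00 becomes −1.81 (0.19 toward zero) |
| Same mechanism, true effect −5 | −5.00 becomes −4.54 (0.46 toward zero) |
| Symptom-related in one arm only (logistic) | 0.80 |
| Symptom-related in one arm only, correlation r with 12-week score | 0.16, 0.33, 0.49, 0.82 for r = 0.1, 0.2, 0.3, 0.5 |

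The last row has a closed form for a normal latent dropout score: shift = r × 6 × φ(1.036)/0.85 = r × 6 × 0.2332/0.85 = 1.646r. In the one-arm rows the direction depends on which arm loses its more symptomatic women.

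**5. Scale against the SE.** With the site counts the SAP reports as contributing data (16 MH, 15 HV, 6 control) and 23 women per site, SE = √[36 × (0.01 + 0.99/23) × (1/k₁ + 1/k₂)]. This is 0.50 for HV − MH and 0.67 for HV − control. A one-arm correlation of 0.2 therefore moves the HV − control contrast by 0.33/0.67, about half an SE.

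**The case against.** The best defence is that the sections can be read together. The 24-week requirement is first stated for the primary model, and the Analytic Dataset sentence nearly repeats it. The Statistical Methods section gives the specific rule for the longitudinal and secondary models. The remark on unbalanced data makes little sense if every woman must have her last visit. This is probably what the authors meant, and a reader should not infer a settled plan to delete earlier data. But the restrictive sentence has no such limit and no text ranks the two rules, so the conflict stands as written.

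Several stronger readings are not supported:

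- *The restricted contrasts are biased.* They can be. The zero rows above are as consistent with the documents as the others.
- *15% of women lose their earlier data.* That is an upper bound; the SAP gives attrition overall, not by visit. Less late attrition would mean smaller shifts.
- *The shifts apply unchanged to the fitted models.* The SAP says it will control for baseline QIDS-SR16. If baseline and 12-week scores correlate at 0.5 (assumed) and dropout depends only on the 12-week score, the adjusted shift is 1 − 0.5 × 0.5 = 0.75 of the figure shown, although the SE falls too.
- *The Randomization Methods section is a further contradiction.* Its statement, "Data collected from all study participants will be used in the analysis", directly follows the account of eight programs dropping out. It most naturally concerns sites, not visits.
- *Nothing guards against dropout.* Multiple imputation and a review of missingness by arm are planned. They soften the consequence, but they do not settle which population the main longitudinal and secondary results use.

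**Conclusion.** The concern holds as a conflict between two stated rules for the longitudinal QIDS-SR16 and secondary-outcome models. The literal restrictive rule gives the worse result. Its cost is about 7% on the SE of the 12-week contrasts if the full 15% attrition falls after 12 weeks. Possible bias ranges from zero to about 0.8 points over the mechanisms shown, all of them assumed.

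A reader might infer that the superiority and non-inferiority decisions are at risk. They are not: for the single-visit 24-week model the two sections agree on who is analysed. What is affected is supportive and secondary, which makes this worth correcting before database lock but not a threat to the main conclusion.

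**What to change.** In the Analytic Dataset section, limit the 24-week requirement to the single-visit primary QIDS-SR16 model. Then add a sentence such as: *The longitudinal QIDS-SR16 and secondary-outcome models use all available data from all participants in randomised sites, analysed as allocated; in practice these are participants with at least one post-baseline value of the outcome.* Report the number analysed per visit and arm in Table 2.

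This keeps the rule already given in Statistical Methods and needs no new data. The one small cost is that the number analysed will differ between the primary and the longitudinal rows, which the reported counts will explain.
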